## LIST OF ABBREVIATIONS AND RELEVANT DEFINITIONS

ABR	ABR form, General Assessment and Registration form, is the application form that is required for submission to the accredited Ethics Committee (In Dutch, ABR = Algemene Beoordeling en Registratie)
AE	Adverse Event
AR	Adverse Reaction
CA	Competent Authority
CCMO	Central Committee on Research Involving Human Subjects; in Dutch: Centrale Commissie Mensgebonden Onderzoek
CV	Curriculum Vitae
DSMB	Data Safety Monitoring Board
EU	European Union
EudraCT	European drug regulatory affairs Clinical Trials
GCP	Good Clinical Practice
IB	Investigator's Brochure
IC	Informed Consent
IMP	Investigational Medicinal Product
IMPD	Investigational Medicinal Product Dossier
METC	Medical research ethics committee (MREC); in Dutch: medisch ethische toetsing commissie (METC)
(S)AE	(Serious) Adverse Event
SPC	Summary of Product Characteristics (in Dutch: officiële productinformatie IB1-tekst)
Sponsor	The sponsor is the party that commissions the organisation or performance of the research, for example a pharmaceutical company, academic hospital, scientific organisation or investigator. A party that provides funding for a study but does not commission it is not regarded as the sponsor, but referred to as a subsidising party.
SUSAR	Suspected Unexpected Serious Adverse Reaction
Wbp	Personal Data Protection Act (in Dutch: Wet Bescherming Persoonsgegevens)
WMO	Medical Research Involving Human Subjects Act (in Dutch: Wet Medisch-wetenschappelijk Onderzoek met Mensen)
DAA	Direct Anterior Approach
PLA	PosteroLateral Approach
NOV	Nederlandse Orthopaedische Vereniging (Dutch Orthopaedic Society)
MIS	Minimal Invasive Surgery
THA	Total Hip Arthroplasty
MCA	Medisch Centrum Alkmaar (Medical Centre Alkmaar)(participating hospital)
VAS	Visual Analogue Scale
OHS	Oxford Hip Score

---

(3D) CT	(3 Dimensional) Computed Tomography
QoL	Quality of Life
MRI	Magnetic Resonance Imaging
EQ-5D	EuroQol 5 Dimensions quality of life test
BMI	Body Mass Index
HOOS	Hip dysfunction and Osteoarthritis Outcome Score
NFU	Dutch Federation of Academic Centers (Nederlandse Federatie van Universitaire centra)

## SUMMARY

**Rationale:** Total hip arthroplasty (THA) is one of the most commonly performed orthopaedic surgeries. Recently, several studies have shown that the surgical approach to the hip known as the anterior or Huter approach could result in faster rehabilitation and more patient satisfaction after THA. The anterior approach allows the surgeon to reach the hip joint from the front, as opposed to the posterolateral approach, in which the joint is reached from the back. This way, no muscles are dissected, and the hip can be replaced without detachment of any muscle from the pelvis or femur. This study aims to compare the direct anterior approach (DAA) with the posterolateral approach (PLA) in patients undergoing uncemented THA. The main focus will be clinical, functional and surgical outcome and cost-effectiveness.

**Objective:** The objective of the study is to compare the DAA for THA with the standard PLA with respect to clinical, functional and surgical outcome and cost-effectiveness among patients, aged over 18 years, needing hip replacement.

**Study design:** The proposed study is a single centre, parallel group randomised clinical trial with balanced randomisation (1:1), and with a follow-up of two years after surgery.

**Study population:** Patients, aged over 18 years, suffering from osteoarthritis, who are a candidate for uncemented THA.

**Intervention (if applicable):** Total hip arthroplasty using the posterolateral and direct anterior approach.

**Main study parameters/endpoints:** The main study parameter of the study is the clinical outcome during the two years of follow-up after surgery. The clinical outcome is defined in terms of pain and function of the hip in relation to different activities of daily life.

**Nature and extent of the burden and risks associated with participation, benefit and group relatedness:** Patients included in the study will follow the regular surgical and rehabilitation protocols. All patients will be asked to fill out several questionnaires at the regular visits to the outpatient clinic and will be send additional questionnaires in between. This will cost no more than 10 minutes each time. The risks involved with the intervention are no different from the normal risks involved with THA. In addition, 15 patients in each treatment group will have one MRI and another 15 in each group one CT scan performed. The study will not provide personal benefits or cause increased pre-, intra- and postoperative risks to the participating patients, but future patients may benefit from the results of the study performed. Ultimately this will result in more insight in total hip arthroplasty.

## 1. INTRODUCTION AND RATIONALE

In the Netherlands, approximately 25.000 total hip arthroplasties (THA) are performed each year . It is estimated that the number of THA procedures will increase to 50.000 per year in 2030. Although there is general agreement about the surgical procedure, there is still debate about the surgical approach to be used to reach the hip joint. In their guideline 'Totale Heup Prothese' (meaning THA), The Dutch Orthopaedic Society (NOV) is not able to indicate one of the approaches as preferable . Of the standard approaches, the posterolateral approach (PLA) is the surgical technique most often used. The hip joint is approached from behind, for which several muscles need to be detached, which requires a healing process. It also may increase the risk of incomplete healing, resulting in pain and a decrease in quality of walking and quality of life.

Currently, there is a strong tendency for surgical techniques to be improved and minimally invasive surgery (MIS) techniques are of interest. MIS is aimed at minimizing local soft-tissue trauma and shortening of hospital stay and rehabilitation time. One of the MIS techniques, the direct anterior approach (DAA), is used more and more for replacing the hip joint. Using the DAA, the hip joint is reached from the front and is replaced through the natural interval between the muscles, with much less muscle damage. Due to minimal soft tissue damage, length of hospital stay and rehabilitation time might be shortened when using the DAA. Also, this approach might result in a faster recovery of gait and mobility, and thus might affect the quality of life of (older) people needing a THA. The DAA is now common practice in a limited number of hospitals in the Netherlands.

The existing evidence with respect to the effectiveness of the DAA is limited. The length of hospital stay was found to be 3-5 days less for the DAA compared to other approaches . Two studies did not find a difference but reported already relatively short stays of 3-4 days . Also, two of three studies found more DAA patients to be discharged home, compared to other approaches . Mainly in the short term, the DAA is associated with less postoperative pain and consumption of pain medication , a faster recovery time  and a more rapid recovery of hip function . After 6 months, however, generally no differences between the DAA and other approaches are found for clinical parameters . In a systematic review, de Verteuil et al.  concluded that DAA for total hip arthroplasty has small peri-operative advantages in terms of blood loss and operation time. They may be associated with a shorter hospital stay and faster recovery.

As a pilot study, we analysed our own patient files for differences between the DAA and PLA in a cohort of patients operated between January 2012 and December 2012 by a single surgeon in our hospital. A total of 80 patients (83 hips) undergoing THA using PLA (N=38) or DAA (N=45) were analysed. Patients operated with the DAA had a significantly shorter LOS ( $p=.009$ ) and 3 times more adequate acetabular cup inclination ( $p=.004$ ). Patients operated with the PLA had shorter operation time ( $p<0.001$ ) and blood loss ( $p<0.001$ ). Complications and follow-up measurements did not show significant differences between the two approaches. Differences between the pre-surgery and 1 year follow-up measurements were also comparable (submitted data).

The innovative character of the present study is that this is the first randomised controlled trial on this topic that will include clinical, functional and surgical outcomes as well as the cost-effectiveness of the DAA compared to standard PLA. Therefore, the results of this study will add knowledge of

effectiveness and economic knowledge of health care costs, not known so far, related to THA. The DAA is relatively new and only performed by a limited number of orthopaedic surgeons in a limited number of hospitals in the Netherlands. This study might resolve the debate whether the DAA or the PLA is the preferred type of surgery. If the DAA proves to be cost-effective, patients, surgeons and society will benefit. Patients will experience health gain by faster recovery and faster discharge to home. Physicians will be able to choose the most efficient intervention. Society will benefit because of a cost-reduction due to less days of hospital stay and shorter rehabilitation time.

## 2. OBJECTIVES

### Primary Objective:

To compare the direct anterior approach (DAA) for Total Hip Arthroplasty (THA) with the standard posterolateral approach (PLA) with respect to clinical outcome among patients needing hip replacement.

[figure not shown]
### Secondary Objectives:

To compare the direct anterior approach (DAA) for Total Hip Arthroplasty (THA) with the standard posterolateral approach (PLA) with respect to functional and surgical outcome and cost-effectiveness among patients needing hip replacement.

### 3. STUDY DESIGN

The proposed study is a single centre (Medisch Centrum Alkmaar, MCA) parallel group randomised controlled trial, with balanced randomisation (1:1 DAA:PLA), with a follow-up of two years after surgery alongside an economic evaluation. The study will take place between 2014 and 2018 in the Medical Centre Alkmaar. The surgical procedures will be performed by three orthopaedic surgeons.

Figure 1: Flow chart of the study design

## 4. STUDY POPULATION

### 4.1 Population (base)

Study participants are patients aged over 18 years, reporting to the outpatient department with clinical and radiographic signs of osteoarthritis of the hip. The surgeon together with the patient will decide if uncemented THA is appropriate. The study will be performed in Medical Centre Alkmaar, where in 2013 665 hip replacements were performed, of which about 80% were uncemented total hip replacements. There are currently three orthopaedic surgeons that perform both the DAA and PLA, who will participate in the current study. Each surgeon performs about 100 total hip replacements each year.

### 4.2 Inclusion criteria

In order to be eligible to participate in this study, a subject must meet all of the following criteria:

- Willing and able to participate in the study protocol;
- Age between 18 and 80 years
- ASA Physical Status I & II
- Diagnosed with osteoarthritis of the hip
- Subjects for who it is decided that they will undergo an uncemented THA at Medical Centre Alkmaar.
- Subjects who are able to give voluntary, written informed consent to participate in this clinical investigation and from whom consent has been obtained.
- Subjects, who, in the opinion of the Clinical Investigator, are able to understand this clinical investigation, cooperate with the investigational procedures and are willing to return for all the required post-treatment follow-ups.

### 4.3 Exclusion criteria

A potential subject who meets any of the following criteria will be excluded from participation in this study:

- Patients with previous surgery to the ipsilateral or contralateral hip;
- Patients with posttraumatic changes of the pelvis or femur;
- Patients with inflammatory arthropathies;
- Patients diagnosed with osteoporosis
- Patients diagnosed with rheumatoid arthritis
- Patients who suffer from insulin dependant diabetes
- Patients who lack understanding of the Dutch language
- Patients who are treated for or diagnosed with neurological or muscle disorders which make assessment of pain and gait not possible

#### 4.4 Sample size calculation

The primary outcome is the clinical outcome. As we expect faster recovery for the DAA compared to the PLA, but an equal outcome in the long term, we want to detect a significant difference at 3 months. We calculated the sample size using the Hip Dysfunction and Osteoarthritis Outcome Score (HOOS) and the VAS score for perceived pain. Both these measurements are included in the Patient Related Outcome Measures (PROMs), which are currently the nationwide standard for the evaluation of orthopaedic treatments in the Netherlands used by hospitals and insurance companies.

The HOOS is a disease specific measure assessing pain and function of the hip in 5 different subscales (symptoms, pain, activities of daily living (ADL), sports & recreation, quality of life). In each subscale patients can score up to 100 points, with 0 points being the worst score and 100 points the best. To detect a clinically relevant difference of 7 points in the HOOS symptoms, pain or ADL subscales and using a standard deviation (SD) of 15 points with a two-sided 5% significance level and a power of 80%, a sample size of 72 patients per group is necessary. To detect a difference in VAS score (0-10) of 1 point, i.e. a score of 2.5 SD 2 for the PLA and 1.5 SD 2 for the DAA with a two-sided 5% significance level and a power of 80%, a sample size of 64 patients per group is necessary. Given an anticipated dropout rate of 20% during the 2-year follow-up, we will recruit 2 times 86 patients, 172 patients in total.

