## 8. METHODS

### 8.1 Study parameters/endpoints

#### 8.1.1 Main study parameter/endpoint

Primary study parameters are the clinical outcome parameters:

- Hip pain and symptoms assessed using the symptoms, pain and activities of daily living (ADL) subscales of the Hip Dysfunction and Osteoarthritis Outcome Score (HOOS) after three months
- Perceived pain in the week before the moment of assessment, assessed using a Visual Analogue Scale (VAS) after three months

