#### 8.1.2 Secondary study parameters/endpoints

Secondary study parameters are the clinical, functional and surgical outcome parameters and cost-effectiveness:

- Hip pain and symptoms assessed using the sports & recreation and quality of life subscales of the Hip Dysfunction and Osteoarthritis Outcome Score (HOOS)
- Length of hospital stay
- Quality of life assessed using the EQ-5D
- Functioning during daily living assessed using the HOOS
- Quality of walking assessed during a timed up and go test and a two times 50m walk using inertial sensors
- Operation time, blood loss, and other parameters of the surgical procedures
- Cup and stem positioning assessed using standard radiography
- Cost-Effectiveness assessed using the cost-questionnaire
- Muscle status assessed using MRI in a sample of 15 patients from each group
- Positioning of the implant assessed using CT scans in a sample of 15 patients from each group.
- All complications related to the surgery and rehabilitation
- Productivity costs
- Direct medical costs (costs of additional radiography, medical consumption)

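### Four unranked primary scores, HOOS and VAS each sized at a full two-sided 5%, have no lead endpoint, testing order or joint rule, and the Summary and section 10.1 do not keep to the three-month primary time point

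*Protocol*

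**What the plan says.** **Primary set.** Protocol section 8.1.1 lists two bullets that hold four scores. The first is "Hip pain and symptoms assessed using the symptoms, pain and activities of daily living (ADL) subscales" of the HOOS, and the second is pain in the past week "assessed using a Visual Analogue Scale (VAS) after three months". Both bullets give three months. Nothing ranks the scores.

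**Sizing.** Section 4.4 aims "To detect a clinically relevant difference of 7 points in the HOOS symptoms, pain or ADL subscales", "using a standard deviation (SD) of 15 points", and concludes: "with a two-sided 5% significance level and a power of 80%, a sample size of 72 patients per group is necessary". VAS is sized separately, from "a score of 2.5 SD 2 for the PLA and 1.5 SD 2 for the DAA", again at two-sided 5% and 80% power, which gives 64 per group. Section 4.4 also places the difference of interest at three months and expects equal results in the long term.

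**Analysis.** Section 10.1 compares the primary parameters after the operation and over follow-up, repeats the comparison on change from the pre-operative value, and adds longitudinal models. It sets no order, no split of the 5% and no rule for combining the four results.

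**Time frame elsewhere.** The Summary states: "The main study parameter of the study is the clinical outcome during the two years of follow-up after surgery".

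**Secondary list.** Section 8.1.2 includes "Functioning during daily living assessed using the HOOS", with no time point, although HOOS ADL is already primary in 8.1.1.

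**The concern.** A 5% level and 80% power describe a trial's main claim only if it is clear which test, or which combination of tests, makes that claim. Here there are four candidate tests, and HOOS and VAS are each sized as if tested alone. Whoever writes the report could choose the success rule after seeing the results, and each available rule has a different error rate or a different power from those stated. The unclear time frame adds to this freedom: sections 4.4 and 8.1.1 fix three months, while the Summary and section 10.1 do not. At stake is whether a claim that the anterior approach is better carries the error rate used to justify the sample size.

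**Working it through.** **Inputs from section 4.4.** HOOS difference 7, SD 15. VAS difference 1, SD 2. Two-sided 5%, power 80%. Allocation is 1:1 (section 3). The protocol gives no correlation between the four scores, so a common correlation ρ is assumed and varied.

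**1. Reproduce the stated sizes.** n per group = 2(z₀.₉₇₅ + z₀.₈₀)²(SD/difference)², with z values 1.960 and 0.842.
- HOOS: 2 × 7.849 × (15/7)² = 72.08, against 72 stated.
- VAS: 2 × 7.849 × (2/1)² = 62.8; the t-test version gives 63.8, against 64 stated.

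A one-sided 5% would give 57 for HOOS, which does not fit. Each calculation therefore uses the full two-sided 5% for a single test.

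**2. If any one score sufficed.** Under independence, the chance of at least one false result is 1 − 0.95⁴ = 0.185. With a common correlation ρ and c = 1.960 it is

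1 − ∫ φ(x) [Φ((c − √ρ x)/√(1−ρ)) − Φ((−c − √ρ x)/√(1−ρ))]⁴ dx.

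**3. If all four had to succeed.** With 72 per group, the expected test statistics are (7/15) × √(72/2) = 2.80 for each HOOS subscale and (1/2) × √(72/2) = 3.00 for VAS. With m_j denoting these means, joint power is

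∫ φ(x) ∏ [1 − Φ((c − m_j − √ρ x)/√(1−ρ))] dx,

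assuming that all four planned differences are real.

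| Assumed ρ | At least one false result (either direction) | Multiple of 5% | Power to win on all four, 72 per group |
|---|---|---|---|
| 0 | 18.5% | 3.7 | not needed here |
| 0.5 | 15.6% | 3.1 | about 57% |
| 0.7 | 13.0% | 2.6 | about 64% |
| 0.8 | 11.4% | 2.3 | about 67% |
| 0.9 | 9.4% | 1.9 | about 71% |

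The error figures count both directions. A false result favouring the anterior approach is about half as likely, for example 13.0%/2 = 6.5% at ρ = 0.7 against a nominal 2.5%, so the multiple is unchanged.

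**4. If the 5% were shared by Holm.** The first step is at 0.05/4 = 1.25%. Power for one HOOS subscale at that step with 72 per group is 61% by the t test (62% by the normal approximation).

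**5. If a fixed order were used.** The first score is tested at the full 5%, so for a HOOS subscale with 72 per group its power stays at the planned 80%. The chance of any false claim stays at or below 5%, because each later test is reached only after a significant result.

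**6. Time frame.** Sections 4.4 and 8.1.1 give three months. The Summary gives two years of follow-up. Section 10.1 names no single time for the primary comparison. These are conflicts in the current text.

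**The case against.** The strongest reply is that the protocol nowhere says one significant score is enough. A reader might infer that rule from the word joining the three HOOS subscales in section 4.4. However, that sentence says which subscales the 7-point and SD 15 assumptions cover, and VAS is handled in a sentence of its own. An unseen statistical analysis plan may also set a joint rule. Sizing each test at 5% is compatible with a valid one, because a fixed order leaves 72 and 64 unchanged. This stands, and it is why the error figures are conditional on a rule that the protocol does not state.

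A reader might also combine the Summary with the questionnaire schedule and count four scores at five follow-up times as primary tests. The documents do not support that. Sections 4.4 and 8.1.1 fix three months, section 4.4 expects no long-term difference, and section 10.1 does not make every time point primary.

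Three smaller points also stand. HOOS pain and VAS pain measure closely related things in the same patients, so independence is an upper bound, and above a correlation of about 0.87 the inflation is below twofold. The 61% under Holm is for the first step only: with all four planned effects present and correlations of 0.5 to 0.8, simulation gives 70% to 71% per HOOS subscale over the whole procedure and 81% to 90% for at least one success. The ADL overlap is a duplicated listing and adds no primary test.

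The reply does not remove the gap. The protocol defines a primary set, fixes its sample size and describes its analysis without saying how the four results answer the primary question. Its statements on the time frame disagree whatever another document says.

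**Conclusion.** The concern holds in a limited form. The protocol leaves the success rule open, and the obvious choices do not all match its stated 5% and 80%. If any one score suffices, error is about 9% to 16% at assumed correlations of 0.9 to 0.5, and 18.5% at the independence bound. If all four are required, error is controlled but joint power is about 57% to 71% over the same correlations. Both ranges rest on an assumed common correlation, and the power figures also assume 72 evaluable patients per group and the planned differences on every score. It would go too far to say that the plan adopts an any-one-suffices rule, or that its error rate is a known multiple of 5%. The conflict over the time frame is certain and needs no assumption. This should be fixed before results are seen. It does not call the design or the sample size into question.

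**What to change.** - **Section 8.1.1:** state a fixed testing order for the four scores at three months, each at two-sided 5%, stopping at the first non-significant result. The sponsor chooses the order on clinical grounds.
- **Alternative:** if the four scores are to count equally, use Holm and restate the power in section 4.4, noting 61% for one HOOS subscale at the 1.25% step with 72 per group.
- **Summary and section 10.1:** align both with the three-month primary time point already in 8.1.1, and label comparisons at other times as secondary.
- **Section 8.1.2:** limit HOOS daily-living function to time points other than three months.

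The cost is protocol wording. With a fixed order, the sample size and the power of the first score are kept. The downside is that a later score cannot be claimed as a primary result if an earlier one fails.

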## **8.4 Withdrawal of individual subjects**

Withdrawal is not to be expected, as a standard implant is being used and follow-up is close to routine follow-up of total hip arthroplasty following the protocol of the Medical Centre Alkmaar. Participants can stop participating in the study at any time for any reason if they wish to do so without any consequences. Patients who withdraw from the study will have the reason for their withdrawal recorded, if given, on the case report forms (CRF's). The postoperative assessments include standard evaluations according to the clinical protocol, so every attempt must be made to ensure that all the participants return for these controls. The researchers and/or the treating specialist involved can decide to withdraw a participant from the study for urgent medical reasons.

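### The 86 per group in section 4.4 does not keep the 72 evaluable patients that HOOS needs if the stated 20% is lost; a 20% loss calls for 90 per group

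*Protocol*

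**What the plan says.** Section 4.4 of the protocol powers the trial for a comparison at 3 months, on two measures.

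- **HOOS:** The target is worded as "To detect a clinically relevant difference of 7 points in the HOOS symptoms, pain or ADL subscales". The assumed spread is an SD of 15 points. The paragraph then concludes that, at 80% power and a two-sided 5% level, 72 patients are needed in each group.
- **VAS pain:** The inputs are a mean of 2.5 under the PLA against 1.5 under the DAA, each with SD 2. Level and power are as for HOOS, and the result is that "a sample size of 64 patients per group is necessary".

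The larger requirement, 72 for HOOS, sets the size of the trial. The allowance for loss follows: "Given an anticipated dropout rate of 20% during the 2-year follow-up, we will recruit 2 times 86 patients, 172 patients in total". The inflation formula is not shown.

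Three other places bear on this. Section 8.1.1 fixes the primary parameters at three months. Section 8.5 says that withdrawn participants are not replaced. Section 8.4 says "Withdrawal is not to be expected, as a standard implant is being used" and adds that follow-up is close to routine.

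**The concern.** An allowance for dropout is meant to leave the required number of patients after the loss has occurred. To do that, the required number is divided by the fraction retained. Multiplying by one plus the dropout rate gives too small a figure, because the loss acts on the enlarged number and not on the original one. The recruited 86 per group looks like the result of that multiplication.

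At stake is the agreement between the headline sample size and the power stated for it. HOOS drives the size, so any shortfall falls on HOOS. As withdrawn patients are not replaced, nothing later in the plan makes up the difference.

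**Working it through.** **Inputs (all from section 4.4):** two-sided 5% level, 80% power, HOOS difference 7 with SD 15, VAS difference 1 with SD 2, dropout 20% over two years, 86 recruited per group. Allocation is 1:1 (section 3).

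**Step 1. Reproduce the evaluable numbers.** For two means, n per group = 2 (z₀.₉₇₅ + z₀.₈₀)² (SD/difference)².

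- HOOS: 2 × (1.96 + 0.84)² × (15/7)² = 72.00. More decimals in the z values give 72.08, and the two-sample t-test gives 73.05. The stated 72 is reproduced within rounding.
- VAS: 2 × (1.96 + 0.84)² × (2/1)² = 62.7; the t-test gives 63.8. The stated 64 is reproduced within rounding.

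**Step 2. Reproduce the recruited number.**

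| Route | Per group |
|---|---|
| 72 × 1.2 | 86.4 |
| 72/0.8 | 90 |
| 64 × 1.2 | 76.8 |
| 64/0.8 | 80 |

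Only the first route gives 86, after rounding down.

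**Step 3. Apply the stated loss to the stated size.** 86 × (1 − 0.20) = 68.8 per group, against 72 required. Retaining 72 needs 72/0.8 = 90 per group, or 180 in total, which is 180 − 172 = 8 more patients.

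**Step 4. Power by loss at 3 months.** With n = 86 × (1 − loss), power by the normal approximation is Φ[(difference/SD) × √(n/2) − 1.96]. For HOOS at n = 68.8: (7/15) × √34.4 − 1.96 = 0.777, and Φ(0.777) = 0.781. The protocol gives no 3-month loss, so the losses below are assumptions that show the range. The 2.8% row assumes a constant rate of loss that reaches 20% at 24 months: 1 − 0.8^(3/24) = 0.028.

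| Loss at 3 months | Evaluable per group | HOOS power, normal (t-test) | VAS power, normal (t-test) |
|---|---|---|---|
| 0% | 86 | 86.4% (86.1%) | 90.6% (90.3%) |
| 2.8% | 83.6 | 85.5% (85.1%) | 89.9% (89.5%) |
| 5% | 81.7 | 84.7% (84.3%) | 89.2% (88.8%) |
| 10% | 77.4 | 82.7% (82.3%) | 87.5% (87.1%) |
| 16.3% | 72 | 80.0% (79.4%) | 85.1% (84.6%) |
| 20% | 68.8 | 78.1% (77.6%) | 83.5% (82.9%) |

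**Step 5. Break-even.** The loss at which 86 still leaves the protocol's own 72 is 1 − 72/86 = 16.3%.

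**The case against.** The strongest reply is that the shortfall joins two time points. The 20% is a two-year figure, while the powered comparison is at three months. HOOS power falls to about 78% only if the whole two-year loss happens in the first three months. Under a constant rate of loss it would be about 85%, and even a 10% loss by three months leaves it above 82%. This stands, and it limits the point. A reader might infer that 172 patients cannot deliver 80% power. The documents do not support that: 172 is enough at any 3-month loss up to about 16%. What the reply does not do is rescue the text, because section 4.4 makes no argument about early loss, gives no 3-month figure and applies the 20% directly to the sample size. The 3-month questionnaire is also sent by mail or email (section 8.3), so a low loss at that point should be stated and not presumed.

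Three further inferences are tempting and should not be drawn.

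- *That 72 is itself an error, or that HOOS and VAS were calculated by different methods.* With z values of 1.96 and 0.84 the HOOS formula gives 72.00. The protocol names no formula for either measure, and 64 also follows from the common shortcut 16/(difference/SD)² = 16 × 4 = 64. VAS does not set the size in any case.
- *That section 8.4 contradicts the 20%.* It concerns withdrawal of individual subjects, whereas a dropout allowance can also cover unreturned questionnaires. The two sit awkwardly together, but both can be true.
- *That adjusting for baseline would restore the power.* How much it would gain depends on a correlation that the protocol does not give.

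**Conclusion.** Wrong as written, minor in size. The stated 86 per group, the stated 20% loss and the stated need for 72 evaluable patients cannot all hold together: 20% off 86 leaves 68.8, and the size that matches is 90 per group. That conclusion needs only the protocol's own three figures. The explanation that 72 was multiplied by 1.2 is an inference from the numerical match.

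The effect on power depends on an assumption that the protocol leaves open. If all 20% are lost by three months, HOOS power is about 78%, roughly 2 percentage points below plan and equivalent to 8 patients in total. VAS power remains at about 83%, above its target. If 3-month loss is at most about 16%, the planned 72 per group are retained and there is no shortfall. The power figures rest on the protocol's own differences and SDs and on equal loss in the two groups. The finding does not threaten the validity of the trial or its error rate.

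**What to change.** Keep 172 and correct the wording of section 4.4:

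1. State that 172 randomised patients give about 78% power for HOOS if 20% are lost, and that 80% power holds if loss at the 3-month primary endpoint is at most about 16%.
2. State the loss assumed at 3 months, with a reason, separately from the 20% over two years.
3. Note that 90 per group (180 in total) is the size that matches a 20% loss.

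The cost is a few sentences and a slightly less favourable power statement for the worst case. No extra enrolment is needed, and neither the design nor the analysis changes.
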